Diabetic nephropathy accounts for the majority of chronic kidney disease. In Japan, it has been the main primary disease leading to the introduction of maintenance dialysis (hemodialysis, peritoneal dialysis) since 1998²⁾ and accounted for 43.7% of the total number of patients on dialysis in 2015.³⁾ In Japan, the total costs of artificial dialysis are around 1.4 trillion yen (2009),⁴⁾ meaning that dialysis accounts for 4% of Japan's total health care costs. Controlling the number of patients who receive dialysis is therefore a significant societal issue. Patients receiving dialysis face many employment and lifestyle restrictions, and the burden on their caregivers (e.g., families) is also considerable. In addition, the five-year survival rate of patients who have been started on dialysis has been reported to be 60.8%.³⁾ Thus, it is important for patients with diabetes to diagnose and treat nephropathy early to inhibit its progression from the viewpoint of the prognosis of patients, the quality of life of patients and caregivers, and health economics. In early (Stage 2) nephropathy, in which the urine albumin level is 30 mg/gCr or above, if treatment is not administered, the urine albumin level will rise at a rate of around 10 to 20% a year until after 10 to 15 years the patient has progressed to overt (Stage 3) nephropathy. The patient's glomerular filtration rate (GFR) will then gradually decrease (by between 2 and 20 mL/min/1.73 m² per year), ultimately resulting in end-stage renal failure (renal failure stage, dialysis therapy stage).⁵⁾ It has been reported that as the urine albumin level increases, the incidence of cardiovascular events increases,^{2,6)} and the prognosis for renal function worsens.⁷⁾ Thus, treatment guidelines recommend starting treatment in the early stage, i.e., early nephropathy stage. In addition, it has been reported that improving blood pressure management even in the overt nephropathy stage can result in remission from macroalbuminuria to normal urine albumin levels, and intensive therapy therefore is believed to be critical for patients with overt nephropathy as well.^{8,9)}

At present, the only drugs that are indicated for diabetic nephropathy in Japan are losartan potassium, an ARB drug the use of which is limited to type 2 diabetes patients with hypertension and proteinuria (urine ACR \geq 300 mg/g), and imidapril hydrochloride, and ACE-I drug the use of which is limited to type 1 diabetes patients.

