3.2 Inclusion Criteria

Patients will be eligible for enrollment in the study if all of the following criteria apply, and the patients are capable of providing consent. Furthermore, the clinical laboratory test values that have been centrally measured at a central laboratory will be used for the inclusion criteria assessments.

- (1) Japanese patients with age \geq 30 years at written informed consent acquisition.
- (2) Patients who have received diagnoses of type 2 diabetes based on the diagnosis criteria of the Japan Diabetes Society by the time of written informed consent acquisition.
- (3) Sex: Either
- (4) Inpatient/outpatient status: Outpatient
- (5) Patients who have been receiving dietary and exercise therapy for diabetes without any changes to the regimens since at least 12 weeks before the first day of the treatment period. However, this restriction will not apply if the exercise therapy cannot be continued because of a complication.
- (6) Patients who have been receiving angiotensin-converting enzyme inhibitor (ACE-I) or angiotensin II receptor blocker (ARB) drugs at the maximum approved dose since at least 5 weeks before the first day of the screening period (or at the maximum approved dose for hypertension if the drug has not been approved for an indication of diabetic nephropathy).

However, this restriction will not apply if the (sub) investigator determines that for medical reasons it would not be appropriate to use the maximum approved dose. Furthermore, the concomitant use of ACE-I and ARB drugs will not be permitted.

- (7) Patients with HbA1c $\geq 6.5\%$ and $\leq 12.0\%$ on the first day of the run-in period.
- (8) Patients with eGFR ≥ 30 mL/min/1.73 m² and < 90 mL/min/1.73 m² on the first day of the run-in period.
- (9) Patients with a median urine albumin/creatinine ratio (urine ACR) for 3 days' worth of first morning void urine collected within 1 week that includes the visit day on the first day of the screening period that is at least 300 mg/g Cr and not more than 5,000 mg/g Cr. Furthermore, if this criterion is not satisfied, the (sub) investigator may perform retesting during the screening period if he/she determines that it is medically appropriate. No rule is being established regarding the number of times retesting may be performed.

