2.3. Randomization Procedures

Subjects will be randomly assigned in a 1:1 ratio to the TA-7284 100 mg tablet group or the TA-7284 tablet placebo group based on stratified randomization, with eGFR on the first day of the run-in period as the stratification factor (≥ 30 and < 45 , ≥ 45 and < 60 , ≥ 60 and < 90).

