2.5. Sample Size Justification

300 subjects (150 subjects per group) as the number of subjects who will start the treatment period

Rationale

3. Endpoints

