7.1.3. Significance Level and Confidence Coefficient

The tests will be all two-sided, with a significance level of 5%. The confidence intervals will be two-sided, and the confidence coefficient will be 95%.

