7.6. Analysis of Efficacy

7.6.1. Primary Endpoints

7.6.1.1. Primary Analysis

Analysis population(s): FAS, PPS

Analysis parameter(s): Proportion of subjects with a decline of 30% in the eGFR at Week 104 of the treatment period

Analysis method:

In accordance with “6.2.2. Tabulation of the eGFR at Each Assessment Time Point When Imputing Data Outside the Allowable Time Window,” a dataset will be prepared using [REDACTED]. The estimated values from this dataset, and the variance thereof, will be combined using Rubin’s rule, and the proportion of subjects with a decline of 30% in the eGFR at Week 104 of the treatment period, and the 95% confidence interval thereof, will be shown for each treatment group. The point estimate for the difference between the groups (placebo group minus TA-7284 group) and the 95% confidence interval according to the Farrington-Manning method will also be shown.

Listings

Analysis population(s): Randomized subjects

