7.6.1.2. Secondary Analysis

Analysis population(s): FAS, PPS

Analysis parameter(s): Proportion of subjects with a decline of 30% in the eGFR at Week 104 of the treatment period

Analysis method:

In accordance with “6.2.2. Tabulation of the eGFR at Each Assessment Time Point When Imputing Data Outside the Allowable Time Window,” a dataset will be prepared using [REDACTED]. The estimated values from this dataset, and the variance thereof, will be combined using Rubin’s rule, and the proportion of subjects with a decline of 30% in the eGFR at Week 104 of the treatment period, and the 95% confidence interval thereof, will be shown for each treatment group.

In addition, for each of these datasets, a logistic regression model will be applied with a decline of 30% in the eGFR at Week 104 of the treatment period as the target variable, treatment group and the stratification factor eGFR on the first day of the run-in period (≥ 30 and < 45 , ≥ 45 and < 60 , ≥ 60 and < 90) as factors, and the urine ACR (first morning void urine) as covariates, and the estimates and variances thereof will be calculated and combined in accordance with Rubin’s rule. An intergroup comparison of these results will be performed, and the odds ratio of a 30% decline in the eGFR in the TA-7284 group relative to the placebo group at Week 104 of the treatment period, and the 95% confidence interval thereof, will be presented.

Listings

Analysis population(s): Randomized subjects

7.6.1.3. Other Analysis 1

Analysis population(s): FAS, PPS

Analysis parameter(s): Proportion of subjects with a decline of 30% in the eGFR at Week 104 of the treatment period

Analysis method:

The proportion of subjects with a 30% decline in the eGFR at Week 104 of the treatment period, and the 95% confidence interval thereof, will be presented for each treatment group for the dataset obtained through the replacement of missing values at Week 104 of the treatment period in accordance with “6.3 Handling of eGFR Data at the End of the Treatment Period.” The point estimate for the difference between the groups (placebo group minus TA-7284 group) and the 95% confidence interval according to the Farrington-Manning method will also be shown.

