7.6.3. Issues in Statistical Analyses

7.6.3.1. Adjustments for Covariates

An analysis using a logistic regression model was performed in “7.6.1.2. Secondary Analysis” and “7.6.1.3. Other Analyses,” and the log-transformed urine ACR level (first morning void urine) on the first day of the treatment period was used as a covariate.

An analysis using a mixed model for repeated measures was performed in “7.6.2.2. Percent Changes

in the Urine ACR (First Morning Void Urine) and Fasted Urine Glucose/Creatinine Ratio,” and the log-transformed value of the analysis parameter on the first day of the treatment period and the interaction between the assessment time point and the log-transformed value of the analysis parameter on the first day of the treatment period were used as covariates.

An analysis using a mixed model for repeated measures was performed in “7.6.2.3. The Change in eGFR, HbA1c, Fasting Blood Glucose, Blood Pressure (Systolic Blood Pressure, Diastolic Blood Pressure), Lipids (HDL-C, Fasting Neutral Lipids), and Body Weight, and the Percent Change in eGFR, Lipids (HDL-C, Fasting Neutral Lipids), and Body Weight,” and the value of the analysis parameter on the first day of the treatment period and the interaction between the assessment time point and the value of the analysis parameter on the first day of the treatment period were used as covariates.

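### The primary risk difference is valid but uses no baseline covariate, although the SAP already models the same outcome on eGFR band and log ACR; if ACR is prognostic, the interval is somewhat wider than it needs to be

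*SAP*

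**What the plan says.** The primary analysis (SAP 7.6.1.1) is placebo minus TA-7284 in the proportion with a 30% decline at Week 104, after multiple imputation. The "95% confidence interval according to the Farrington-Manning method will also be shown". No covariate or stratum is named, and Protocol 13.3.2 specifies the same unadjusted comparison.

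The secondary analysis (SAP 7.6.1.2) fits a logistic model to the same outcome, with arm and run-in eGFR band "as factors, and the urine ACR (first morning void urine) as covariates". SAP 7.6.1.3 repeats the model with missing Week 104 values counted as declines. Both report an odds ratio from it. SAP 7.6.3.1 names both analyses and states that "the log-transformed urine ACR level (first morning void urine) on the first day of the treatment period was used as a covariate". Protocol 13.3.2 had listed randomisation factors only; ACR was added in the SAP.

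ACR does not reach the overall risk difference by another route:
- SAP 2.3: "Subjects will be randomly assigned in a 1:1 ratio", stratified on run-in eGFR in three bands only.
- SAP 6.2.2: the imputation regression names eGFR values by visit and nothing else.
- SAP 7.6.3.8: the ACR subgroups (up to 1000, above 1000) give two separate differences, not one adjusted difference.

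On prognosis, Protocol section 1(1) says that as urine albumin rises "the prognosis for renal function worsens". Entry requires a screening ACR of "at least 300 mg/g Cr and not more than 5,000 mg/g Cr" (Protocol 3.2, criterion 9).

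**The concern.** Adjusting for a baseline predictor by standardisation estimates the same marginal risk difference with less variance. It also removes the part of the observed difference that is due to chance imbalance in that predictor. Here the predictor is collected and the model is planned, yet the result is reported only as a conditional odds ratio, which is a different measure and cannot stand in for the primary risk difference. If the arms differed by chance in albuminuria, the plan would offer no adjusted difference for the full FAS against which to read the primary result. What is at stake is some precision and a clear reading of the main comparison.

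**Working it through.** **Plan's own figure.** SAP 2.5 gives "300 subjects (150 subjects per group) as the number of subjects who will start the treatment period"; its rationale is blacked out. With two-sided alpha of 5% (SAP 7.1.3) and assumed risks, 150 per arm gives 68% power for 20% vs 10%, 80% for 25% vs 12.5%, and 88% for 30% vs 15%. The figure of 300 is neither confirmed nor contradicted.

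**Inputs from the documents.** 150 per arm, 1:1, ACR 300 to 5,000 mg/g. **Assumed.** Risks of 20% vs 10%, 30% vs 16% and 40% vs 25%; ln(ACR) uniform over the entry range; a range of odds ratios (OR) for ACR. The assumed SD of ln(ACR) is ln(5000/300)/√12 = 2.813/3.464 = 0.81, so an OR of 2 per ln unit is 2^0.81 = 1.76 per SD.

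**Large-sample calculation.** Let m0 and m1 be the risks given ln(ACR) under placebo and TA-7284. At 1:1 allocation the variance of the standardised difference, relative to the unadjusted one, is

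1 − Var(m1 + m0) / (2[p1(1−p1) + p0(1−p0)]).

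For 30% vs 16% the unadjusted half-width is 1.96 × √[(0.21 + 0.1344)/150] = 9.39 points. With adjustment:

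| OR per ln unit (per SD) | Variance ratio | Half-width, points | Equivalent N |
|---|---|---|---|
| 1.0 (1.00) | 1.000 | 9.39 | 300 |
| 1.5 (1.39) | 0.982 | 9.31 | 306 |
| 2 (1.76) | 0.950 | 9.15 | 316 |
| 3 (2.44) | 0.887 | 8.85 | 338 |
| 4 (3.08) | 0.837 | 8.59 | 358 |

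Over the three risk pairs, the gain at OR 2 to 3 per ln unit equals 11 to 48 extra subjects on top of 300.

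**Simulation, OR per SD of log ACR.** The first variance column has no eGFR bands, a treatment OR of 0.5 and placebo risk 20%/30%. The second includes eGFR bands and a delta-method interval. Both use complete data.

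| OR per SD | Variance ratio, no bands | Variance ratio, with bands | Fall in SD, with bands (1 − √ratio) |
|---|---|---|---|
| 1.5 | 0.978/0.970 | 0.97-0.99 | 0.5-1.5% |
| 2.0 | 0.947/0.934 | 0.93-0.96 | 2-4% |
| 3.0 | 0.865/0.847 | 0.84-0.87 | 7-8% |

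The mean difference did not change (for example 0.114 vs 0.114 without bands). Coverage with the bands and the delta-method interval was 94-95.5%.

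**Against the actual Farrington-Manning interval** (2,000 trials per scenario, no bands). For 30% vs 16%, mean width was 0.188, against 0.186, 0.183 and 0.177 adjusted at OR 1.5, 2 and 3 per ln unit. At OR 3, power rose from 82.9% to 87.7%. At OR 1 the empirical variance ratio was 1.004-1.006 over the three risk pairs, so adjusting for a useless covariate costs almost nothing. For 20% vs 10% the adjusted interval was 1.2% narrower even at OR 1. That reflects the type of interval, not ACR, so the variance ratios are the cleaner measure.

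**Chance imbalance.** The arm difference in standardised log ACR has SE √(2/150) = 0.115, so a 1.96-SE imbalance is 0.226 SD. The shift in the raw difference is roughly 0.226 × ln(OR) × mean p(1−p). With mean p(1−p) of 0.125 (20% vs 10%) to 0.172 (30% vs 16%), that is 2.0-2.7 points at OR 2 per SD and 3.1-4.3 at OR 3. These are slightly overstated, because averaging over ACR flattens the slope.

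**The case against.** An unadjusted primary analysis with an adjusted secondary one is a legitimate choice, and the protocol and SAP state it consistently. A reader might infer that the primary interval is wrong or under-covers. It does not: under randomisation the unadjusted difference is unbiased, and its interval already allows for chance imbalance on average.

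A reader might also infer that the trial is too imprecise, or that albuminuria is ignored. The first cannot be shown, because the sample-size rationale is not visible. The second is not so. ACR-adjusted odds ratios are planned for the 30% and 40% endpoints, the difference is shown by ACR subgroup, and baseline ACR is tabulated by arm (SAP 7.3).

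The size rests on an assumption. The study cited for renal prognosis is, by its title in the reference list, a type 1 diabetes cohort. If ln(ACR) is uniform, the entry range spans √12 = 3.46 SD. An OR of 3 per SD then implies 3^3.46, about 45-fold odds across it, against about 11-fold at OR 2 and 4-fold at OR 1.5. The upper end therefore looks extreme. Missing data and imputation variance were not simulated, and overlap between ACR and eGFR band would reduce ACR's own contribution. All of this stands and keeps the point modest.

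It is also tempting to say that the SAP leaves the ACR scale undefined. SAP 7.6.3.1 names both logistic analyses and settles it as log-transformed, so only the wording of 7.6.1.2 and 7.6.1.3 needs aligning. Nor can complete baseline ACR be taken for granted: SAP 4.11 provides for two or one values instead of three, and 6.1 provides for missing ones.

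**Conclusion.** The point holds as a worthwhile gain in precision, not as the correction of an error. The primary interval is valid, but it leaves out information the trial already collects and the SAP already models. If ACR is prognostic, standardising on the planned model reduces the SD of the estimate by about 1-4% at an OR of 1.5-2 per SD of log ACR, and by about 8% at 3.0. These odds ratios and the event risks are assumptions; the documents give neither. With no prognostic effect there is no gain and essentially no loss. The benefit for the primary interval itself comes only if the standardised difference becomes the primary estimate. Reported beside it, the adjusted difference helps interpretation but does not narrow the primary interval.

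**What to change.** 1. In SAP 7.6.1.1, pre-specify the standardised risk difference from the logistic model already planned (arm, run-in eGFR band, log ACR on the first day of the treatment period). In each imputed dataset, average the predicted risks of all FAS subjects under placebo and under TA-7284, take the difference with a delta-method variance, and pool by Rubin's rule. Do the same for the 40% endpoint.
2. Keep the unadjusted Farrington-Manning interval as a supporting analysis. Record the departure from Protocol 13.3.2, with its reason, in SAP section 9, as Protocol 13.4 requires for changes before database lock.
3. If the sponsor keeps the protocol's primary method, report the standardised difference as a named analysis beside it and accept that the primary interval is not narrowed.
4. Add log baseline ACR to the imputation model in 6.2.2, so that the imputation and analysis models agree, a missing baseline ACR is imputed, and no FAS subject is dropped.
5. Align 7.6.1.2 and 7.6.1.3 with 7.6.3.1: log-transformed ACR, first day of the treatment period.

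The cost is SAP wording, a few lines of code on a model already planned, and, under steps 1 and 2, a documented change of primary method. No new data are needed. The choice should be fixed before unblinding, since an adjusted difference added later would carry little weight.

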7.6.1.2. Secondary Analysis

Analysis population(s): FAS, PPS

Analysis parameter(s): Proportion of subjects with a decline of 30% in the eGFR at Week 104 of the treatment period

Analysis method:

In accordance with “6.2.2. Tabulation of the eGFR at Each Assessment Time Point When Imputing Data Outside the Allowable Time Window,” a dataset will be prepared using [REDACTED]. The estimated values from this dataset, and the variance thereof, will be combined using Rubin’s rule, and the proportion of subjects with a decline of 30% in the eGFR at Week 104 of the treatment period, and the 95% confidence interval thereof, will be shown for each treatment group.

In addition, for each of these datasets, a logistic regression model will be applied with a decline of 30% in the eGFR at Week 104 of the treatment period as the target variable, treatment group and the stratification factor eGFR on the first day of the run-in period (≥ 30 and < 45 , ≥ 45 and < 60 , ≥ 60 and < 90) as factors, and the urine ACR (first morning void urine) as covariates, and the estimates and variances thereof will be calculated and combined in accordance with Rubin’s rule. An intergroup comparison of these results will be performed, and the odds ratio of a 30% decline in the eGFR in the TA-7284 group relative to the placebo group at Week 104 of the treatment period, and the 95% confidence interval thereof, will be presented.

Listings

Analysis population(s): Randomized subjects

7.6.1.3. Other Analysis 1

Analysis population(s): FAS, PPS

Analysis parameter(s): Proportion of subjects with a decline of 30% in the eGFR at Week 104 of the treatment period

Analysis method:

The proportion of subjects with a 30% decline in the eGFR at Week 104 of the treatment period, and the 95% confidence interval thereof, will be presented for each treatment group for the dataset obtained through the replacement of missing values at Week 104 of the treatment period in accordance with “6.3 Handling of eGFR Data at the End of the Treatment Period.” The point estimate for the difference between the groups (placebo group minus TA-7284 group) and the 95% confidence interval according to the Farrington-Manning method will also be shown.

An intergroup comparison using a logistic regression model will be performed with a decline of 30% in the eGFR at Week 104 of the treatment period as the target variable, treatment group and the stratification factor eGFR on the first day of the run-in period (≥ 30 and < 45 , ≥ 45 and < 60 , ≥ 60 and $<$

90) as factors, and the urine ACR (first morning void urine) as covariates. Thereafter, the odds ratio of a 30% decline in the eGFR in the TA-7284 group relative to the placebo group at Week 104 of the treatment period, and the 95% confidence interval thereof, will be presented.

Listings

Analysis population(s): Randomized subjects

7.6.1.4. Other Analysis 2

Analysis population(s): FAS, PPS

Analysis parameter(s): Proportion of subjects with a decline of 30% in the eGFR at Week 104 of the treatment period

Analysis method:

The proportion of subjects with a 30% decline in the eGFR at Week 104 of the treatment period, and the 95% confidence interval thereof, will be presented for each treatment group in accordance with “6.2.1 Tabulation by eGFR Assessment Time Point.” The point estimate for the difference between the groups (placebo group minus TA-7284 group) and the 95% confidence interval according to the Farrington-Manning method will also be shown.

Listings

Analysis population(s): Randomized subjects

7.6.2. Secondary endpoints

7.6.2.1. The proportion of subjects achieving a 40% decline in the eGFR

Analysis population(s): FAS, PPS

Analysis parameter(s): Proportion of subjects with a decline of 40% in the eGFR at Week 104 of the treatment period

Analysis method: Analyses similar to those described in 7.6.1.1, 7.6.1.2, 7.6.1.3, and 7.6.1.4 will be performed for these analysis parameters.

Listings

Analysis population(s): Randomized subjects

7.6.2.2. Percent Changes in the Urine ACR (First Morning Void Urine) and Fasted Urine

Glucose/Creatinine Ratio

Analysis population(s): FAS

Analysis parameter(s): Urine ACR (first morning void urine), fasted urine glucose/creatinine ratio

Analysis method:

For the data described in “6.2.3. Tabulation of Endpoints Other Than the eGFR and Urine ACR at Each Assessment Time Point” and “6.2.4. Tabulation of the Urine ACR Endpoints at Each Assessment Time Point,” for each analysis parameter at each assessment time point in each group, the geometric mean and 95% confidence interval at the start of the treatment period and at follow-up (Week 108) (Week 104 for the fasted urine glucose/creatinine ratio) will be presented. For each treatment group, time profiles will be prepared showing the geometric mean and 95% confidence interval thereof along the y-axis and each measurement time point up through Week 104 along the x-axis. In addition, for the log-transformed values of each assessment parameter for each treatment group, the mean change and 95% confidence interval at each assessment time point from the first day of the treatment period through follow-up (Week 108) (Week 104 for the fasted urine glucose/creatinine ratio) will be calculated. These values will be inverse transformed, and the geometric mean and 95% confidence interval of the ratio for each assessment parameter will be presented.

For the data described in “6.2.3. Tabulation of Endpoints Other Than the eGFR and Urine ACR at Each Assessment Time Point” and “6.2.4. Tabulation of the Urine ACR Endpoints at Each Assessment Time Point,” the mean changes in the log-transformed values of each analysis parameter at each assessment time point from Week 4 to Week 104 will be analyzed in a mixed model for repeated measures using a restricted maximum likelihood (REML) approach, with treatment group, assessment time point, treatment group—assessment time point interaction, and the stratification factor of the eGFR on the first day of the run-in period (≥ 30 and < 45 , ≥ 45 and < 60 , ≥ 60 and < 90) as factors, and the log-transformed values of the assessment parameters on the first day of the treatment period and the interactions between the assessment time points and the log-transformed values of the assessment parameters on the first day of the treatment period as covariates. For each treatment group at each assessment time point, the LS mean and standard error, 95% confidence interval, difference between the groups (the TA-7284 group minus the placebo group) in the LS mean, and the standard error and 95% confidence interval thereof, will be calculated. Additionally, the LS means and 95% confidence intervals of the changes in the log-transformed values will be back-transformed, and the geometric LS means and 95% confidence intervals of the ratios of each analysis parameter will be presented. The values obtained from the following formula will be presented as the percent change from baseline: (geometric LS mean of the ratio in the analysis parameter – 1) $\times 100$. Also, the differences between the groups (the TA-7284 group minus the placebo group) in the LS means, and the 95% confidence intervals thereof, will be back-transformed, and the ratios of the geometric LS means of the ratios of the analysis parameters, and the 95% confidence intervals and P values, will be presented. The percent changes relative to placebo [(ratio of the geometric LS means of the ratio of each analysis parameter – 1) $\times 100$] will also be presented.

The Kenward-Roger method will be used to adjust the degrees of freedom, and an unstructured covariance structure will be used for within-subject error modeling.

However, in within-subject error modeling, if the model fails to converge when using an unstructured covariance matrix, the covariance matrix will be changed according to the following procedure, and the first covariance matrix with successful convergence will be used to perform the analysis.

Heterogeneous Toeplitz (TOEPH) → Heterogeneous AR(1) (ARH(1)) → Heterogeneous CS (CSH) → Toeplitz (TOEP) → First-order autoregressive (AR(1)) → Compound symmetry (CS)

Listings

Analysis population(s): Randomized subjects

7.6.2.3. The Change in eGFR, HbA1c, Fasting Blood Glucose, Blood Pressure (Systolic Blood Pressure, Diastolic Blood Pressure), Lipids (HDL-C, Fasting Neutral Lipids), and Body Weight, and the Percent Change in eGFR, Lipids (HDL-C, Fasting Neutral Lipids), and Body Weight

Analysis population(s): FAS

Analysis parameter(s): eGFR, HbA1c, fasting glucose, blood pressure (systolic blood pressure, diastolic blood pressure), lipids (HDL-C, fasting neutral lipids), body weight

Analysis method:

For the data in “6.2.1. Tabulation by eGFR Assessment Time Point” and “6.2.3. Tabulation of Endpoints Other Than the eGFR and Urine ACR at Each Assessment Time Point,” for each treatment group, descriptive statistics will be provided for the values of each assessment parameter both on the first day of the treatment period (for the eGFR, this will be the mean of the value obtained on the first day of the run-in period and the value obtained on the first day of the treatment period) and at each of the assessment time points until follow-up (Week 108) (Week 104 for all parameters other than the eGFR and HbA1c). For each treatment group, the mean change and standard deviation at each assessment time point from the first day of the treatment period (for the eGFR, the mean of the value on the first day of the run-in period and the value on the first day of the treatment period) until follow-up (Week 108) (Week 104 for all of the parameters other than the eGFR and HbA1c) will be calculated for each of the eGFR, HbA1c, fasting glucose, blood pressure (systolic blood pressure, diastolic blood pressure), lipids (HDL-C, fasting neutral lipids), and body weight. Also, for each treatment group, the mean percent change and standard deviation at each assessment time point from the first day of the treatment period (for the eGFR, the mean of the value on the first day of the run-in period and the value on the first day of the treatment period) until follow-up (Week 108) (Week 104 for all of the parameters other than the eGFR and HbA1c) will be calculated for each of the eGFR, lipids (HDL-C, fasting neutral lipids), and body weight.

For the data in “6.2.1. Tabulation by eGFR Assessment Time Point” and “6.2.3. Tabulation of

Endpoints Other Than the eGFR and Urine ACR at Each Assessment Time Point,” each of the mean changes at each assessment time point from Week 4 to Week 104 in the eGFR, HbA1c, fasting glucose, blood pressure (systolic blood pressure, diastolic blood pressure), lipids (HDL-C, fasting neutral lipids), and body weight, and the mean percent changes at each assessment time point from Week 4 to Week 104 in the eGFR, lipids (HDL-C, fasting neutral lipids), and body weight will be analyzed in a mixed model for repeated measures using a restricted maximum likelihood (REML) approach, with treatment group, assessment time point, treatment group—assessment time point interaction, and the stratification factor of the eGFR on the first day of the run-in period (≥ 30 and < 45 , ≥ 45 and < 60 , ≥ 60 and < 90) as factors, and the values of the assessment parameters on the first day of the treatment period and the interactions between the assessment time points and the values of the assessment parameters on the first day of the treatment period as covariates. The LS means and standard errors at each measurement time point for each treatment group will be presented. The differences between the groups in the LS mean (the TA-7284 group minus the placebo group) and the 95% confidence intervals and P values will also be presented. In addition, time profiles will be prepared for each treatment group for each of the mean change and the mean percent change, with the LS means and standard errors, calculated based on MMRM, along the y-axis and each measurement time point up through Week 104 along the x-axis.

The Kenward-Roger method will be used to adjust the degrees of freedom, and an unstructured covariance structure will be used for within-subject error modeling.

However, in within-subject error modeling, if the model fails to converge when using an unstructured covariance matrix, the covariance matrix will be changed according to the following procedure, and the first covariance matrix with successful convergence will be used to perform the analysis.

Heterogeneous Toeplitz (TOEPH) → Heterogeneous AR(1) (ARH(1)) → Heterogeneous CS (CSH) → Toeplitz (TOEP) → First-order autoregressive (AR(1)) → Compound symmetry (CS)

Listings

Analysis population(s): Randomized subjects

